3.2 Discussion of Study Design, including the Choice of Control Groups

Part A is designed as a single dose, parallel group study to evaluate the safety and terminal PK profile of a range of doses of RPL554 in a new DPI formulation compared to placebo. The safety and bronchodilatory response following a single dose will also be assessed.

In Part A, five dose levels ranging from 150 µg up to 6000 µg have been selected to evaluate the safety, PK and efficacy/pharmacodynamic characteristics of this formulation over a dose range covering a 40-fold increase in doses. A total of approximately 36 COPD patients aged 40 to 80 years (inclusive) will be randomized. Patients in Part A will be randomly assigned to receive either RPL554 or placebo via DPI. Following an analysis of the safety, PK and efficacy/pharmacodynamics, four doses will be selected for Part B. Study medication administered via DPI will be double blind, except for the 6000 µg treatment arm in Part A which

will be single blind due to the number of capsules required, in order to minimize any potential bias in the overall assessment of treatment effect and safety.

Part B is designed as a crossover study to assess the steady state efficacy/pharmacodynamic effect of four dose levels of RPL554 administered by DPI after a week of twice daily dosing, and to compare that effect with placebo DPI. Steady state PK and safety will also be assessed. One week of treatment was selected to evaluate efficacy/pharmacodynamics, PK and safety at steady state, as clinical data to date has shown that steady state PK is achieved after approximately 3 days of twice-daily dosing with the nebulized formulation.

In Part B, all patients from Part A will undergo five treatment periods in a double-blind randomized, crossover design; therefore, each patient will act as his or her own control. This design makes it possible to obtain unbiased inferences about differences between treatments, based on intra-patient differences.

The washout period between the treatment periods has been selected based upon the available PK of RPL554 in healthy volunteers, and patients with asthma or COPD. Five half-lives is considered as the time for elimination of RPL554 from the body. In this study, a washout period of 7 to 10 days from the last dose of study medication has been deemed adequate to ensure there was no overlap between the PK profiles of treatments with RPL554 in consecutive treatment periods.

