Summary statistics for each parameter will be presented for baseline, at point of interest (if applicable) and change from baseline by treatment group on patients with both assessments, on the original scale.

Document: Z:\RPL554\AZA40375\Biostatistics\Documentation\SAP\Verona RPL554-DP-201 SAP v2.0 – Part B

Author: [name] / [name]

Version Number: 2.0

Version Date: [08JUL2019]

Template No.: CS_TP_BS016 Revision 5

Reference: CS_WI_BS005

Effective Date: 01Apr2018

Copyright © 2009, 2010, 2012, 2016, 2018 IQVIA. All rights reserved. The contents of this document are confidential and proprietary to IQVIA Holdings Inc. and its subsidiaries. Unauthorized use, disclosure or reproduction is strictly prohibited.

15.2.3.2. Analysis of Secondary Variable 7

Onset of action will be summarized by treatment and a Kaplan-Meier plot illustrating time to onset constructed. The SAS® procedure LIFETEST, will be used as follows to calculate the median, 25th and 75th percentile:

```
PROC LIFETEST DATA=... OUTSURV =... CONFTYPE = LINEAR METHOD =  
KM ALPHA = 0.05 ALPHAQT = 0.05 PLOTS = (SURVIVAL (FAILURE NOCENSOR));  
    TIME ONSET*STATUS (1);  
    STRATA TREATMENT;  
RUN;
```

where ONSET = time to onset of action

TREATMENT = treatment group (Respective dose of RPL554, 150 μ g, 500 μ g, 1500 μ g and 3000 μ g)

STATUS (1) = indicates an event of onset of action

To calculate the mean difference to RPL554 3000 μ g, the SAS procedure LIFETEST will be carried for each treatment comparison pair individually.

If a patient does not have onset of action from pre-dose on Day 1 over the next 120 minutes (2 hours) the data will be censored at 120 minutes or if a patient prematurely discontinued before 120 minutes, the last available assessment time post-dose (1 indicates censored variables). Median differences to the highest dose (RPL554 3000 μ g) will be estimated and the p-value based on the PROC LIFETEST above (Wilcoxon signed rank sum test) between each treatment groups and the highest dose will also be presented.

15.2.3.3. Analysis of Secondary Variable 8

As described in [section 4.3](#), this SAP will not summarise the analyses related to the PK concentrations and parameters and this will be handled by a third-party vendor.

15.2.3.4. Analysis of Secondary Variable 9

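### Part B onset-of-action comparisons use an independent-groups Wilcoxon test on crossover data but call it a signed rank test; if a patient's onset times are positively correlated, p-values are too large and power is lost

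*SAP*

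**What the plan says.** Protocol 3.2 sets Part B up as a crossover over five treatment periods; "therefore, each patient will act as his or her own control". Onset (SAP Part B 15.2.1.3) is a rise of more than 10% in FEV₁ from pre-dose on Day 1. It is read at 5, 15, 30, 60, 90 and 120 minutes and censored at 120 minutes, and placebo is left out.

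SAP Part B 15.2.3.2 runs PROC LIFETEST with "STRATA TREATMENT" as the only grouping, separately for each dose paired with 3000 µg. It reports "the p-value based on the PROC LIFETEST above (Wilcoxon signed rank sum test").

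The same section contradicts itself twice:

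- **Censoring code.** The legend reads "STATUS (1) = indicates an event of onset of action". The TIME statement, "TIME ONSET*STATUS (1"), and a later remark, "1 indicates censored variables", both make 1 the censored value.
- **Effect measure.** One sentence begins "To calculate the mean difference to RPL554" 3000 µg; a later one begins "Median differences to the highest dose".

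Protocol 9.4.5 plans a summary, a Kaplan-Meier plot and median times for onset. The dose comparisons it describes are expressed as geometric mean ratios, so they concern the FEV₁ parameters. SAP Part B 3.3 records no change from the protocol.

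**The concern.** The words and the code describe different tests. Following the code ignores the pairing. Following the words leaves no rule for times censored at 120 minutes, which a signed rank test needs. Elsewhere the SAP respects the crossover: the FEV₁ models in 15.1.3 and 15.2.3.1 have a random patient effect, and the dyspnea and pulse analyses adjust for patient. Onset is the exception, and no reason is given.

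Onset of action is a stated secondary objective. If fast responders at one dose tend to be fast at another, an independent-groups variance overstates the uncertainty of the comparison, and a real difference between doses is more easily missed. The legend slip is separate: a data set built to the legend would swap events and censored times.

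**Working it through.** **The plan's own figure.** The only power statement (Protocol 9.5) is for peak FEV₁: 30 patients, residual CV 6%, 80% power for a 4.6% difference. As a within-patient comparison, SE = 0.06 × √(2/30) = 0.01549 and ln(1.046) = 0.04497, a ratio of 2.90. A noncentral t on 29 df gives power 80.1%, so the figure reproduces. There is no corresponding figure for onset.

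**Direction, by formula.** Let the rank scores at two doses have variance σ² and within-patient correlation ρ. Their difference has variance 2σ²(1 − ρ), while the independent-groups formula uses about 2σ². The planned Z then has null SD √(1 − ρ), and a nominal 5% test has true size 2Φ(−1.96/√(1 − ρ)):

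- ρ = 0: 5.0%
- ρ = 0.3: 2Φ(−2.34) = 1.9%
- ρ = 0.5: 2Φ(−2.77) = 0.6%
- ρ = 0.7: 2Φ(−3.58) = 0.03%
- ρ = −0.3: 2Φ(−1.72) = 8.6%

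So the test is conservative only under positive correlation; under negative correlation it is anti-conservative.

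**Size of the effect, by simulation.**

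- From the documents: 30 patients, the reading times, censoring at 120 minutes, two-sided 5%.
- Assumed, because the documents give none: log-normal onset with median 30 minutes and log SD 1.2, a 1.8-fold slower onset at the lower dose, no period effect, and the correlations shown.
- Planned test: Gehan-Wilcoxon with the independent-groups hypergeometric variance.
- Paired test: Prentice-Wilcoxon scores from the pooled data of the two doses, Z = Σdᵢ / √Σdᵢ², where dᵢ is patient i's score difference.
- 20,000 runs per setting; simulation error about 0.15 points on size and 0.35 on power.
- Censoring: 12% under the null, 25% in the slower arm.

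| Correlation | 0 | 0.3 | 0.5 | 0.7 |
|---|---|---|---|---|
| Size, planned | 4.9% | 2.2% | 0.8% | 0.1% |
| Size, paired | 4.7% | 4.5% | 4.8% | 4.6% |
| Power, planned | 44% | 43% | 42% | 40% |
| Power, paired | 42% | 54% | 66% | 84% |
| Paired minus planned | −2 | +11 | +24 | +44 |

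The simulated sizes sit slightly above the formula because fixed reading times and censoring weaken the correlation between scores.

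**Sensitivity** (power, planned against paired, at correlation 0.3 / 0.5 / 0.7):

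- Median onset 10 minutes: 41 / 41 / 39% against 52 / 65 / 82%.
- Log SD 0.8: 79 / 83 / 88% against 86 / 94 / 99%.
- Log SD 1.6: 23 / 20 / 16% against 33 / 42 / 59%.
- Different assumptions (medians 20 and 40 minutes, log SD 1.5, log shift 0.8): 47–49 / 48–49 / 47–49% against 58–60 / 71–73 / 87–89%. Planned size there is 2.3%, 0.8–1.1% and 0.1%, and about 8% at correlation −0.3.

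**The case against.** **Little hangs on it.** These are secondary comparisons between active doses, and under positive correlation the error creates no false claims. The size of the loss is assumption-driven: at log SD 0.8 the gain from pairing is only 7, 11 and 11 points. All of this is true and limits the weight of the point. It does not make the test match its name or the design.

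**Heavy censoring.** SAP Part B 15.2.1.3 drops the Kaplan-Meier output if more than 50% of patients are censored. With an assumed median of 90 minutes, a 1.8-fold slower dose is about 60% censored, and a difference in medians usually cannot be estimated. This stands as a gap that the revised text should close. It does not affect the choice of a paired test.

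**Hierarchy.** SAP Part B 7.4 calls secondary tests nominal but also says they follow a dose hierarchy. That hierarchy is against placebo, which onset excludes, so its application here is unclear. If it is meant to apply, a count of false positives over three unadjusted comparisons does not describe the plan.

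**Period effects.** The FEV₁ models adjust for period; the Prentice-Wilcoxon test does not. With an assumed 1.8-fold period effect on onset, the paired gain at correlation 0.3 / 0.5 / 0.7 falls to 7 / 17 / 34 points. At 3.3-fold it is about −1 / 4 / 12. Each treatment occurs twice in every period across the ten sequences in SAP Part B Appendix 1, so the comparison is not biased, but a large period effect would remove much of the gain.

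**Conclusion.** The concern holds. That the code is unpaired, that it does not give the named test, and that the legend and the effect measure each contradict themselves follows from the documents alone. That p-values are too large, on average, needs positive within-patient correlation, which is plausible because the same patient is judged by the same FEV₁ criterion in each period, but which the documents do not quantify. Under the main assumptions the loss is about 11, 24 and 44 points of power at correlation 0.3, 0.5 and 0.7, and none at 0. The direction is firm; the size rests on the assumed correlation, onset distribution, shift and absence of a period effect.

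The Kaplan-Meier medians per dose and the primary analysis do not change. The legend error bites only if the data set follows the legend. The unrecorded addition of dose comparisons is a documentation point, since Protocol 9.1 describes its section as a summary.

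**What to change.** In SAP Part B 15.2.3.2, replace the LIFETEST comparison with, for example:

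> Onset time at each lower dose will be compared with RPL554 3000 µg by the paired Prentice-Wilcoxon test, in patients with an observed or censored onset time in both periods.

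Then:

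- Keep the LIFETEST code for the Kaplan-Meier plot and quantiles.
- Use the difference in medians as the one effect measure, since Protocol 9.4.5 plans medians, and delete the mean difference. Say what is reported when a median is not reached or the 50% censoring rule applies.
- Correct the legend so that STATUS = 1 means censored.
- Record the added dose comparisons in SAP Part B 3.3, and say whether the hierarchy in 7.4 applies to them.

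If a sizeable period effect is expected, a frailty or robust-variance model with period is an alternative.

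The cost is SAP wording and a short program, with no new data. There are three downsides:

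- At correlation 0, about 2 points of power are lost.
- A patient with only one of the two periods drops out of that comparison. With 4 of 30 such patients, power at correlation 0 / 0.3 / 0.5 / 0.7 is 37 / 47 / 59 / 78% paired against 41 / 39 / 38 / 36% planned.
- With size restored to 5%, three unadjusted comparisons sharing the 3000 µg data give at least one false positive about 12% of the time, against 12 / 6 / 2 / 0.4% for the planned test at the same correlations.

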15.3. EXPLORATORY EFFICACY

15.3.1. EXPLORATORY EFFICACY VARIABLES & DERIVATIONS

15.3.1.1. Evaluation of dose response of RPL554 on peak and average FEV1 AUC_{0-12h} after morning dose on Day 7, and morning trough FEV1 prior to the last dose on Day 7

The association of dose response for the primary and secondary endpoints listed in this section title will be handled by a third-party vendor.

15.3.1.2. Change from baseline in Likert dyspnea scale measured after morning dose on Day 7

An 11-point Likert scale will be utilized, with patients being asked the following question by a blinded member of staff: “On a scale of zero to ten, please rate your current shortness of breath, with zero indicating no shortness of breath and ten indicating the worst shortness of breath that you can imagine”. This scale will be an instantaneous measurement of their dyspnea at that moment, and not reflective. It will be administered on Day 7 pre-dose and 30 minutes, 1, 1.5, 2, 4, 8, 11 and 12 hours post-dose of each treatment period. Baseline will be considered the pre-dose assessment on Day 1 of each treatment period and change from baseline will be assessed at each timepoint on Day 7.

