2.2.3 Exploratory Objectives

[figure not shown]
- To assess the dose response of RPL554 on peak FEV₁ and average FEV₁ AUC_{0-12h} after morning dose on Day 7, and morning trough FEV₁ prior to the last dose on Day 7
- To examine the effect of RPL554 administered by DPI on a Likert dyspnea scale

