6.4.1 Day 1 of Each Treatment Period

6.4.1.1 *Pre-dose Assessments*

The following assessments will be performed prior to dosing:

- Assess concomitant medications and confirm that medications were withheld as required
- Counsel/remind patient of daily dosing schedule as needed
- Question for adverse events
- Dyspnea scale

- PK sampling
- Blood samples for laboratory safety tests (hematology and blood chemistry)
- Urine pregnancy test (women of childbearing potential only)
- Urinalysis
- 12-lead ECG
- Vital signs
- Brief physical examination (see Section 7.4.5)
- Spirometry; 1 hour (± 5 minutes) and immediately (within 5 minutes) pre-dose
- Inhalation training
- Dispense inhaler, study medication and rescue medication
- At Treatment Period 1 only, assign randomization number from next in sequence available at the study center

6.4.1.2 *Study Medication Administration*

Patients will be dosed once with either RPL554 or placebo according to the randomization scheme. The first two doses of study medication on Day 1 will be administered in the clinic. The second dose will be administered 12 hours (± 10 minutes) after the first dose

6.4.1.3 *Post-dose Assessments*

The following assessments will be performed, at the times indicated relative to dosing:

- Vital signs at 1, 2, 4, 8 and 12 hours (± 10 minutes)
- Dyspnea scale at 30 (± 10) minutes and 1, 1.5, 2, 4, 8 and 12 hours (the latter assessments all ± 15 minutes)
- PK sampling at 15 (± 10) and 30 (± 10) minutes and 1, 1.5, 2, 4, 8 and 12 hours (the latter assessments all ± 15 minutes)
- Spirometry at 5 (± 2), 15 (± 5) and 30 (± 10) minutes and 1, 1.5, 2, 4, 8 and 12 hours (the latter assessments all ± 15 minutes)
- Question for adverse events
- Weigh rescue medication canister
- Dispense study medication to patient

Patients will be discharged from the study center after the 12-hour assessments and instructed to return 6 days later for Day 7. Patients will be contacted by phone the night before the Day 7 visit to remind them to: 1) take their study medication in the evening of Day 6 and record the time, 2) withhold study medication prior to the visit the next day, 3) return their medication during the visit and 4) follow other medication and activity restrictions as described in Section 5.8.1 and 6.1.

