6.4.2 Day 7 of Each Treatment Period

6.4.2.1 *Pre-dose Assessments*

The following assessments will be performed prior to dosing:

- Collect study medication
- Weigh rescue medication canister
- Assess study medication compliance (see Section 5.10);
- Assess concomitant medications; confirm that medications were withheld as required and record time of prior evening dose of study drug
- Question for adverse events
- Dyspnea scale
- PK sampling
- Blood samples for laboratory safety tests (hematology and blood chemistry)
- 12-lead ECG
- Vital signs
- Brief physical examination (see Section 7.4.5)
- Spirometry; 1 hour (± 5 minutes) and immediately(within 5 minutes) pre-dose

6.4.2.2 *Study Medication Administration*

Patients will be dosed once with either RPL554 or placebo according to the randomization scheme.

6.4.2.3 *Post-dose Assessments*

The following assessments will be performed, at the times indicated relative to dosing:

- Vital signs at 1, 2, 4, 8 and 12 hours (± 10 minutes)
- Dyspnea scale at 30 (± 10) minutes and 1, 1.5, 2, 4, 8, 11 and 12 hours (the latter assessments all ± 15 minutes)
- PK sampling at 30 (± 10) minutes and 1, 1.5, 2, 4, 8 and 12 hours (the latter assessments all ± 15 minutes)
- Spirometry at 30 minutes (± 10) and 1, 1.5, 2, 4, 8, 11 and 12 hours (the latter assessments all ± 15 minutes)
- Question for adverse events

Patients will be discharged from the study center after the 12-hour assessments and instructed to return as follows: 1) for all but the final treatment period, 7 to 10 days later for Day 1 of the next treatment period, 2) for the final treatment period, 4 to 10 days later for the End of Study visit.

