9.3.2.2 Secondary Endpoints

- Safety and tolerability:
 - Continuous monitoring of adverse events
 - Laboratory safety tests (hematology, blood chemistry and urinalysis)
 - 12-lead ECG (including QTcF and heart rate), supine vital signs (blood pressure and pulse rate)
- Change from baseline in (morning) trough FEV₁ measured prior to morning dosing on Day 7
- Change from baseline in peak FEV₁ measured after first dose
- Change from baseline in average FEV₁ AUC_{0-4h} measured after morning dosing on Day 7
- Change from baseline in average FEV₁ AUC_{0-12h} measured after first dose and after morning dosing on Day 7
- Determination of onset of action (>10% increase in FEV₁ from pre- to post- first dose, censored at 120 minutes) after first dose
- RPL554 steady state pharmacokinetics (AUC_{0-12h}, C_{max}, t_{max}, accumulation ratio) after dose 13 on Day 7
- Change from baseline in peak pulse after first dose on Day 1 and after morning dosing on Day 7
- Change from baseline in average FEV₁ AUC_{0-4h} and average FEV₁ AUC_{0-12h} on Day 1
- Change from baseline in rescue medication use

9.3.2.3 *Exploratory Endpoint*

- Evaluation of dose response of RPL554 on peak and average FEV₁ AUC_{0-12h} after morning dose on Day 7, and morning trough FEV₁ prior to the last dose on Day 7
- Change from baseline in Likert dyspnea scale measured after single dose and after morning dose on Day 7

9.4 *Statistical Methods*

In general, unless stated otherwise, continuous variables will be summarized using descriptive statistics (number of patients, mean, standard deviation, median, minimum and maximum values) and for categorical (nominal) variables, the number and percentage of patients will be used.

All hypothesis testing will be done using two-sided alternative hypotheses. P-values less than 5% will be considered statistically significant.

9.4.1 *Patient Disposition*

The number of patients enrolled, randomized, completed or withdrawn (with reason for withdrawal) will be summarized.

9.4.2 *Protocol Deviations*

All protocol deviations collected will be divided into critical, major or minor categories. Prior to database lock protocol deviations will be reviewed and consequences for inclusion of patients in various analysis population sets determined and documented.

9.4.3 *Demographics and Other Baseline Characteristics*

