In Part B, change in Likert dyspnea scale to each time point will be compared between the treatments using analysis of covariance models adjusting for factors for treatment, period and patient, and using the pre-dose Day 1 baseline value as a covariate. Additive models will be used for dyspnea.

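### The Part B SAP summarises and models dyspnea on Day 7 only, leaving out the Day 1 comparison that the protocol lists as an exploratory endpoint, and declares no change from protocol

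*SAP*

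**What the plan says.** **Protocol.** The objective in Section 2.2.3 is not tied to a day: "To examine the effect of RPL554 administered by DPI on a Likert dyspnea scale". The matching Part B endpoint in Section 9.3.2.3 names two occasions: "Change from baseline in Likert dyspnea scale measured after single dose and after morning dose on Day 7". Section 6.4.1.3 sets the Day 1 post-dose schedule, "Dyspnea scale at 30 (± 10) minutes and 1, 1.5, 2, 4, 8 and 12 hours", and Section 6.4.1.1 adds a pre-dose score. Section 6.4.2.3 sets the Day 7 schedule, "Dyspnea scale at 30 (± 10) minutes and 1, 1.5, 2, 4, 8, 11 and 12 hours", again with a pre-dose score (6.4.2.1). The analysis text in Section 9.4.5 has no restriction by day: "In Part B, change in Likert dyspnea scale to each time point will be compared between the treatments using analysis of covariance models".

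**SAP Part B.** The title of 15.3.1.2 repeats the protocol endpoint without its single-dose component. The text describes the scale as given on Day 7 at pre-dose and eight post-dose times. Day 1 enters only as the pre-dose baseline, and "change from baseline will be assessed at each timepoint on Day 7". Section 15.3.3 limits the summaries to the Day 7 times. It then specifies an additive ANCOVA for the change from baseline, and the only such change defined is the Day 7 one. Section 3.3, on changes to the analysis from the protocol, reads as none. The SAP states that it is based on protocol version 2.0.

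**The concern.** The protocol names a treatment comparison and schedules the data for it, but the SAP never carries it out. With Section 3.3 reporting no changes, someone reading only the SAP or its output would not know that one occasion of a named endpoint had been left out.

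Two things are at stake. First, Protocol 9.1 requires any departure from the planned analysis to be detailed and justified in the study report, and a departure that the SAP does not recognise is easily missed there. Second, if the Day 1 comparison were added after unblinding, it would look post hoc even though the protocol had specified it in advance.

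The two occasions also answer different questions: response to the first dose of a period, and response after a week of twice-daily dosing. One does not substitute for the other.

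**Working it through.** No power or sample size figure bears on this point, so there is no figure of the plan's own to reproduce. The check compares the texts and counts time points.

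**1. What the single dose refers to.** The phrase stands in the Part B endpoint list, yet elsewhere the protocol uses it for Part A. The Part A schedule (Table 5) and the Part A visit procedures (Section 6.3) contain no dyspnea assessment, and the Part A SAP has no dyspnea analysis. The Part A reading would therefore give an endpoint with no data. The remaining reading is the first dose on Day 1 of each Part B period, for which Section 6.4.1.3 schedules scores.

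**2. Whether Day 1 is analysed elsewhere in the SAP.** It is not. The Part B SAP retains Day 1 for peak FEV₁, both average FEV₁ measures and onset of action (15.2.1.2 and 15.2.1.3) and for peak pulse (16.4). No section covers Day 1 post-dose dyspnea.

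**3. Whether the SAP worked from superseded protocol text.** This does not explain the gap. The SAP cites protocol version 2.0, and its Day 7 list uses the 11-hour time introduced by the amendment.

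**4. Count per treatment period.**

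| Occasion | Times with a change from baseline | Count | In SAP 15.3 |
|---|---|---|---|
| Day 1 | 30 min, 1, 1.5, 2, 4, 8, 12 h | 7 | No |
| Day 7 | pre-dose, 30 min, 1, 1.5, 2, 4, 8, 11, 12 h | 9 | Yes |
| Total | | 16 | 9 of 16 |

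- Share omitted: 7 / 16 = 43.75%, about 44%.
- Active-versus-placebo contrasts with four doses: 16 × 4 = 64 in total, of which 7 × 4 = 28 are omitted.
- Scores per patient over five periods: 7 × 5 = 35.
- In 30 patients: 35 × 30 = 1,050, assuming that all 30 complete every period with no missing scores.

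**5. Sensitivity of the count.** The 15-minute cell in the dyspnea row of Table 6 cannot be read reliably in the available text, so the count uses the list in Section 6.4.1.3. If a 15-minute score were also scheduled on Day 1, the omitted share would be 8 / 17 = 47%.

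**The case against.** **Wording.** The same endpoint list says first dose for FEV₁, onset and pulse, so single dose for dyspnea might mean something else. Reading it as Day 1 of each Part B period is indeed an inference. It stands because the alternative has no data behind it.

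**The data are not lost.** SAP Appendix 1 calls for all CRF variables with data to appear in listings, and Protocol 9.4.8 says in general terms that available data will be listed and summarised. The SAP's output templates (Section 8) are not available to check. This limits the point: what the SAP text lacks is the Day 1 summary and treatment comparison, not every form of reporting. A reader might infer that half the endpoint goes unreported. The documents do not support that, since the raw scores should be listed and the omitted share by time point is 7 of 16.

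**Day 7 is what Part B is for.** Protocol 3.2 describes Part B as an assessment of steady-state effect, and the primary endpoint is on Day 7. This could be a good reason to restrict the dyspnea analysis, but the SAP does not give it.

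**Day 1 as the better comparison.** A reader might also infer that Day 1 is cleaner because its baseline is from the same morning, and that the Day 7 change is weakened by a baseline six days old. The documents do not support this. Protocol 9.4.5 prescribes the Day 1 pre-dose baseline for dyspnea and for FEV₁ alike, including the primary analysis. That choice is not a defect of the dyspnea plan and has no bearing on the omission.

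**Consequence.** The endpoint is exploratory and lies outside the fixed-sequence procedure in SAP 7.4, and a count of unused scores does not show that any conclusion would change. This stands in full and sets the weight of the point.

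**Conclusion.** The mismatch holds as a minor alignment point. Following the SAP exactly would leave a protocol-specified comparison undone at 7 of 16 post-baseline time points per period while stating that nothing had changed.

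This rests on two assumptions: that the single dose in Protocol 9.3.2.3 is the first dose of each Part B period, and that the Section 6.4.1.3 list is the operative Day 1 schedule. The first is the only workable reading. The second affects the count but not the conclusion.

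The primary analysis, alpha and power are unaffected. Nothing in the documents shows that the omission was deliberate. The SAP's retention of Day 1 for FEV₁, onset and pulse is at least compatible with a drafting slip.

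**What to change.** Extend SAP Part B 15.3.1.2 and 15.3.3 to the Day 1 post-dose times: 30 minutes and 1, 1.5, 2, 4, 8 and 12 hours. Restore the single-dose component to the title of 15.3.1.2, stating that it means the first dose of each treatment period. Use the additive ANCOVA already specified, with treatment, period and patient in the model and the Day 1 pre-dose score as covariate. The order in which the two days are presented does not matter.

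If the restriction to Day 7 is intended, state it with its reason in SAP 3.3 and carry it into the study report as Protocol 9.1 requires.

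The cost of the first option is a few lines of SAP text and one more table from data already scheduled for collection, with no new model. The second costs a sentence or two. Either should be settled before Part B is unblinded.
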